## 5.4.4 Other Subject Instructions

The subject should maintain a consistent lifestyle throughout the study regarding exposure to external factors that may produce an exacerbation of their acne. These factors include, but are not limited to, excessive exposure to UV radiation (occupational exposure to the sun, sunbathing, tanning salon use, phototherapy, etc.). Subjects should avoid excessive sun exposure, wind and cold, as much as possible during the study. The subject will be instructed to apply the Cetaphil® Dermacontrol Moisturizer with SPF30 on the face every morning, and re-apply to the face and other exposed skin when sun exposure is expected. Subject should use protective apparel (e.g, hat) when sun exposure cannot be avoided. Avoid sunless tanning products for the duration of the study. Extra care should be taken to wear protective clothing and sunglasses and avoid sun exposure from 10 AM to 3 PM.

Cosmetics may generally be used during the study, but not on study visit days (or must be removed at least 30 minutes prior to study visit). Non-comedogenic cosmetics (cosmetics that do not cause acne) may be used as well as eye and lip makeup. Cosmetics can be applied after the study drug has dried. Foundation make-up is allowed on the days of study visits as long as subjects wash their face at least 30 minutes prior to the study visit. Use of moisturizing foundation will be acceptable during the study if subject has a history of safe usage of the foundation.

GALDERMA R&D RD.06.SPR.204245 V00 18AUG2021 Page 42 of 104

Topical study drug should be applied approximately 1 hour before or 1 hour after application of any other permitted skin care products (e.g. cosmetic products).

Products containing alcohol, alpha hydroxy or glycolic acids and astringents should not be used during the study.

Face shaving is allowed during the study. Male subjects with excessive facial hair that would interfere with acne assessments, as judged by the investigator, are not eligible to participate in the study. Male subjects with facial hair will be expected to keep areas well-groomed prior to study visits, as judged appropriate by the investigator, to perform the acne assessments.

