### Table 4: List of Prohibited Medications/Therapies During Study

### **Topical treatments on the face:**

- Corticosteroids, antibiotics, benzoyl peroxide, azelaic acid, alpha hydroxyl acids, salicylic acid, zinc containing treatments, other anti-acne treatments or other acne treatments (e.g., salicylic acid treatments)
- Retinoids
- Cosmetic/aesthetic procedures on the face (e.g., comedo extraction, desquamating or abrasive agents, adhesive pore cleansing strips)
- Wax epilation
- Photodynamic therapy
- Laser therapy, microdermabrasion, deep chemical peel, plastic surgery for acne
- Agents with potential drying effects on the skin: i.e. antibacterial soaps, astringents, other alcohol-containing topical preparations
- Use of tanning booths or lamps, as well as sunless tanning products for the duration

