### **Systemic treatments:**

- Initiate use of combined oral contraceptives (estrogens and progesterone), implantable/injectable contraceptives, hormonal contraceptive vaginal rings or change of dose (of existing medication)
- Initiate use of combined oral contraceptives approved as acne treatments (e.g., Ortho Tri-Cyclen®, Yaz®, Diane-35®), or change of dose (of existing medication)
- Corticosteroids (except locally acting corticosteroids such as inhaled or intrathecal), antibiotics (except penicillin G and V)
- Oral retinoids / isotretinoin
- Cyproterone acetate / chlormadinone acetate
- Spironolactone
- Immunomodulators
- Vitamin A supplements exceeding the recommended daily allowance (4000 5000 IU)
- Prescription testosterone therapy (e.g., testosterone cypionate, testosterone enanthate, testosterone pellet, testosterone undecanoate) or on a testosterone booster or prescription testosterone (e.g., DHEA, Omnadren®, Sustanon®, testosterone cypionate, testosterone enanthate, testosterone propionate, testosterone phenylpropionate) or testosterone supplements (e.g., Tribulus)
- Anticoagulants and Methoxyflurate

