## a) Rechallenge with Assigned Topical Study Medication

- 1. After all signs and symptoms of AESI have resolved and after a minimum of two weeks from last topical dose application, perform a rechallenge test with the assigned topical study drug. Scheduling on a Monday or Tuesday is ideal, as it ensures the 48-hour and 72-96 hour follow-up assessments occur on weekdays (Table 10).
- 2. Ensure the subject has not been under any treatment with corticosteroids or antihistamines of any route of administration the Week before testing.
- 3. Ensure that the skin on the back has not been exposed to the sun or artificial ultraviolet sources the Week before testing.
- 4. Apply an appropriate quantity of the assigned topical study drug to fill in the cupule of the test chamber to a naïve zone on the back either the right or left side of the center line (or the inner forearm if the back cannot be tested). If no test chamber is available on site, patch test units will be provided by the Sponsor or designee. Apply an empty test chamber as a control for the rechallenge test with assigned topical study drug (note: an empty test chamber will not be needed for ingredient testing, if such test is warranted, as the Sponsor/designee will provide one or more controls for testing). The use of semi-occlusive conditions depends on the irritant potential of the study product and the intensity of the reaction that was observed. The method to be used should be discussed with the Medical Monitor.

Choose a skin site that was not previously involved in the inflammatory skin reaction. Cover the test chamber for 48 hours with a hypoallergenic tape.

- 5. Subject should be informed about avoiding exercise, showers, application of toiletries products, etc., to keep the test system dry
- 6. After 48 hours, remove the test chamber and evaluate the site and take photos after each reading (Table 10):

- at approximately 30 minutes after patch test removal (1st reading) and,
- 24 to 48 hours later (i.e., 72 or 96 hours after application) (2nd reading).
- If the result of the second reading is equivocal, the Investigator or at the Sponsors request, may perform an optional 3rd reading at 96 to 120 hours later (i.e., 6 to 7 days after application of the patch).
- Pictures of each reading and the reading results should be sent to Parexel Pharmacovigilance and medical monitor.

**Table 10:** Patch Testing Readout Schedule

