### **Table 12:** Investigator Overall Conclusion of Suspected Sensitization

	Sensitization Reaction						
0	Negative (absence of reaction or might be irritant reaction)						
1	Equivocal						
2	Positive						

- 8. In case of absence of negative reaction, the subject may resume study treatment if appropriate. Otherwise, the subject should complete end of study procedures.
- 9. If the rechallenge with assigned topical study medication is positive or equivocal, notify Parexel Pharmacovigilance and medical monitor immediately. Except in specific situations, ingredient patch testing of the topical study medication will be initiated as directed by the Sponsor (with individual ingredients at different concentrations if applicable, and possibly negative and positive controls) after a minimum of an additional two weeks (but not later than 6 months) and after all signs and symptoms have resolved.
  - The Sponsor will provide a letter to the investigator with blinded results for ingredient testing, and further instructions how the subject and his/her primary care provider can determine test results, while maintaining blinding of the investigator and site staff (Appendix 14.6).

Note: Ingredient testing will follow the above process beginning with step number 4, with testing of the individual ingredients (and controls, as applicable). The Sponsor or designee will provide the necessary supplies for ingredient testing. Given the delay when ingredient testing supplies may arrive, subjects may receive treatment for their acne other than the study drug, and should stop all acne therapy a minimum of 1 Week before ingredient testing.

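### Ingredient patch testing starts at step 4, so the one-week steroid, antihistamine and UV conditions of steps 2 and 3 are not carried over

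*Protocol*

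**What the plan says.** Protocol 6.3.6.2.4 a) lists nine numbered steps for the rechallenge with the assigned cream. Two of them set conditions for the week before the patch:

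- Step 2: "Ensure the subject has not been under any treatment with corticosteroids or antihistamines of any route of administration the Week before testing".
- Step 3: "Ensure that the skin on the back has not been exposed to the sun or artificial ultraviolet sources the Week before testing".

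If the rechallenge is positive or equivocal, step 9 calls for ingredient testing, directed by the Sponsor, "after a minimum of an additional two weeks (but not later than 6 months) and after all signs and symptoms have resolved". The Note below step 9 defines the procedure: "Ingredient testing will follow the above process beginning with step number 4, with testing of the individual ingredients (and controls, as applicable". It lets subjects take other acne treatment while they wait for supplies, but they "should stop all acne therapy a minimum of 1 Week before ingredient testing".

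Other rules bear on the same exposures:

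- Table 4, which applies during the study, bars topical corticosteroids on the face. Its systemic entry reads "Corticosteroids (except locally acting corticosteroids such as inhaled or intrathecal". It also bars "Use of tanning booths or lamps, as well as sunless tanning products for the duration".
- Section 5.4.4 says "Subjects should avoid excessive sun exposure, wind and cold, as much as possible during the study", and adds protective clothing and avoidance of midday sun.
- Section 3.1 says patients will be told to avoid sun during the study, without limiting this to excessive exposure.
- Table 4 does not list antihistamines, and 5.4.12.4 authorizes whatever is not prohibited.

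**The concern.** The protocol treats two exposures as unacceptable in the week before the rechallenge. It then describes a second patch test of the same kind on the same subject and starts it after the steps that exclude those exposures. A site that follows the Note literally may test ingredients in a subject who took an antihistamine the day before.

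Such an exposure is foreseeable. Ingredient testing is reached only after a skin reaction, and 5.3.4 asks the investigator to ensure suitable therapy when an adverse event leads to discontinuation. It is an inference, though a reasonable one, that this therapy may include an antihistamine or a steroid.

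The stake is individual safety follow-up. If a reaction were suppressed, the responsible ingredient could go unidentified. Appendix 14.8 advises a visit to a primary care physician only when an ingredient result is positive or equivocal, so that advice would not be given.

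**Working it through.** The plan gives no figure to reproduce. The check compares the texts, then looks at timing and size.

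**1. What is carried over**

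| Condition before the rechallenge | Restated for the ingredient test? | Other cover during the study | Stated cover after exit |
|---|---|---|---|
| Step 1: waiting time, signs resolved | Yes, in step 9 | not needed | Step 9 |
| Step 2: corticosteroids, any route | No | Systemic (locally acting routes exempt) and facial topical use, by Table 4 | Only a steroid used as acne therapy, by the Note |
| Step 2: antihistamines, any route | No | None | None |
| Step 3: artificial UV on the back | No | Tanning booths and lamps, by Table 4 | None |
| Step 3: sun on the back | No | General instructions in 3.1 and 5.4.4, but no one-week check of the back | None |

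Patches go on the back, or on the inner forearm if the back cannot be used (step 4), so a ban on facial steroids does not protect the test site.

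**2. Does the check at rechallenge carry forward?** Take the rechallenge patch as day 0. Steps 2 and 3 then cover days -7 to 0. Ingredient testing starts at least two weeks later, at day 14 or after, so its own preceding week is days 7 to 14 at the earliest. The two weeks do not overlap and lie at least 7 days apart. Meeting the conditions once says nothing about the second test.

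**3. Can the test fall after study exit?** Now take day 1 as the first application.

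- Step 1 requires at least two weeks from the last dose, so the earliest rechallenge is day 1 + 14 = day 15.
- Counting the limit from the rechallenge, with 6 months taken as 24 weeks as in Protocol 5.5, the latest ingredient test is day 15 + 168 = day 183. With 182 days it is day 197.
- The last in-window Week 24 visit is day 169 (SAP 4.2.6) + 5 days (schedule of assessments) = day 174.

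Even for the earliest rechallenge, permitted testing extends past the final visit. This holds whether or not step 8, whose wording is unclear, ends participation sooner. The calculation shows only that testing after exit is allowed. It does not show how often it would happen.

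**4. How many subjects?** The prescribing information in Appendix 14.9 lists allergic dermatitis among reactions seen in more than one subject but in under 1% of 1220 treated in the 12-week trials.

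- Range: 2 to 12 subjects, because 1% of 1220 is 12.2.
- Rates: 2/1220 = 0.16% and 12/1220 = 0.98%.
- Expected among 60 active subjects: 60 × 2/1220 = 0.10 to 60 × 12/1220 = 0.59.

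This is not an upper limit. The trigger in 6.3.6.1.3 is suspicion of an allergic contact reaction, which is broader than the label term. Treatment here lasts 24 weeks, and no vehicle rate is given. In the other direction, only some of these subjects would have a positive or equivocal rechallenge, then an ingredient test, and then an uncovered exposure in the week before it. The documents give no figure for that fraction, so none is applied.

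**The case against.** The strongest reply is that the protocol surrounds this test with other protection.

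- **Sun.** Sections 3.1 and 5.4.4, the lamp ban in Table 4 and exclusion criterion 12 together cover most of step 3 while the subject is in the study. This stands. A reader might infer that the back is left open to sun throughout, and the documents do not support that.
- **After exit.** A reader might also infer that nothing protects the test once the study is over. That is wrong too. The one-week acne-therapy stop still applies and would catch a steroid used for acne. The Sponsor directs the test, and the method is to be discussed with the Medical Monitor. Step 4 promises one or more controls, although step 9 says only that a positive control is possible. Photographs and readings are sent for review under step 6. These safeguards are real, but none states the conditions of steps 2 and 3.
- **Visibility of medication.** Concomitant therapies are reviewed at each visit (5.4.12.3) and must be available in the data system when an adverse event of special interest is reported (6.3.6.2.3). This makes in-study antihistamine use visible. It does not bar such use, and it does not extend to a test after exit.
- **A suppressed result would show itself.** An all-negative ingredient panel after a positive whole-product rechallenge would look odd. This is a fair point, but weaker after an equivocal rechallenge. The oddity would not identify the ingredient, and the section provides for no repeat test.
- **The harm is not documented.** The protocol gives no reason for steps 2 and 3, so suppression of a reaction is inferred. This stands, and it limits what can be claimed.

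**Conclusion.** The omission is certain on the text: the Note starts at step 4, step 9 replaces only step 1, and nothing elsewhere restricts antihistamines or locally acting or non-facial steroids before an ingredient test. Because the Note names its starting step, this is a stated rule and not merely missing detail.

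The consequence is small and less certain. Probably 0 or 1 subjects are affected. That judgement rests on the label range of 0.10 to 0.59 expected events in the active arm, which is not an upper limit, and on the further steps needed before the gap matters.

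A reader might infer that the trial's safety results are compromised. The documents do not support this. By the time of ingredient testing, study drug has been stopped, the event has been reported and the reaction to the whole product is on record. Protocol 6.3.6.1.3 and SAP 4.11.2 define the adverse event of special interest by suspicion, so its count does not depend on the ingredient result. No efficacy analysis uses the test. The matter is confined to identifying the ingredient for that subject, and the change is a cheap optional improvement.

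**What to change.** In the Note under step 9 of 6.3.6.2.4 a), change the starting step from 4 to 2. Nothing then conflicts, because step 9 already supplies the timing that replaces step 1. The edit is one number in one sentence. Its cost is an occasional ingredient test postponed by about a week, within the existing 6-month limit. The efficacy analysis is unaffected.

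A separate, optional edit is to word step 3 in terms of the skin at the test site instead of the back, since step 4 allows the inner forearm. That smaller gap affects the rechallenge as well and does not depend on the main change.

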### b) In case of suspicion of immediate contact skin reaction (such as urticaria)

A case-by-case approach will be applied and the procedure to follow will be discussed with the Sponsor.

### 6.3.6.2.5 Procedures for Reporting Pregnancies

Any pregnancy occurring during clinical trials, where the fetus could have been exposed to the study drug, must be monitored until its outcome in order to ensure the complete collection of safety data.

If a subject becomes pregnant, the Investigator is to do the following:

- 1. Immediately inform Parexel Pharmacovigilance of the event by fax or email (Section 6.3.6.2.2).
- 2. Withdraw the subject from the clinical trial.

3. Complete the Pregnancy Surveillance Form – Part I: History and Start of Pregnancy, provided by the Clinical Research Associate (CRA) at the beginning of the clinical trial, as fully as possible. Inform Parexel Pharmacovigilance of the pregnancy by sending this pregnancy form along with the Exit Form within 24 hours to Parexel Pharmacovigilance (see Section 6.3.6.2.2).

- 4. Monitor and record the progress of the pregnancy until its outcome. Contact the subject's regular physician (general practitioner or gynecologist) or hospital staff to obtain further details and ask for regular follow-up information.
- 5. Inform Parexel Pharmacovigilance of the progress by trimonthly updates until the final outcome of the pregnancy, within 24 hours of receiving updates. If the subject can no longer be reached (lost to follow-up), documentation of the nonresponse/contact with two telephone calls and a letter (certified with return receipt) is required.
- 6. At the outcome of the pregnancy, complete the Pregnancy Surveillance Form Part II: Course and Outcome of Pregnancy, as fully as possible. Send this pregnancy form to Parexel Pharmacovigilance within 24 hours (see Section 6.3.6.2.2).
- 7. Any pregnancy with serious complications, spontaneous or therapeutic abortion, ectopic pregnancy, stillbirth, neonatal death, congenital anomaly, or birth defect must be recorded and reported within 24 hours in accordance with the procedure for reporting SAEs. (see 6.3.6.2.2) Section.

### 7 PLANNED STATISTICAL ANALYSES

### 7.1 Statistical Analysis Plan

A statistical analysis plan (SAP) will be developed and issued as a separate document. The SAP will contain a more detailed and technical description of specific data conventions, calculations and of statistical procedures for executing the analysis strategies. The SAP will be finalized prior to the database lock.

Any change from the protocol will be justified and fully documented.

If the blind review suggests changes to the principal features stated in the protocol, these have to be documented in a protocol amendment. Otherwise, it will suffice to update the statistical analysis plan with the considerations suggested from the blind review.

Post hoc exploratory analyses will also be clearly identified in the Clinical Study Report (CSR).

### **7.2** Sample Size Calculation

The sample size calculation is based on the results of the paper "Tazarotene Cream for Post-Inflammatory Hyperpigmentation and Acne Vulgaris in Darker Skin: A Double-Blind, Randomized, Vehicle-Controlled Study" (Grimes 2006).

Trifarotene cream and tazarotene cream are both products indicated for the topical treatment of acne and have similar profiles in terms of tolerability. The study above was used as a basis for comparison in order estimate sample sizes for this study.

α		Power		~	Samp	le Size	Drop out (%)	op Randomised		
(2-sid	ed)	(%)	μDiff	$\sigma_{Diff}$	Trifa	Vehicle		Trifa	Vehicle	Total
0.0	5	90%	-1.0	1.4	42	42	~30%	60	60	120

Considering a two-sided  $\alpha$ =0.05, 90% power, a difference in the sample means of -1.0, a standard deviation of difference of 1.4, a 1:1 allocation ratio between trifarotene cream and vehicle cream and a proportion of drop-outs around 30%, approximately 120 subjects (60+60) are planned to be randomized.

## 7.3 Populations Analyzed, Evaluability and Limitation / Evaluation of Bias

The Intention-to-Treat (ITT) population will be used for the analyses of efficacy endpoints on the face. The Per Protocol (PP) population will be used for a sensitivity analysis of the primary endpoint. The Safety population (SAF) will be used for all safety analyses.

## 7.3.1 Intent-to-treat (ITT) population

The ITT population is defined as all randomized subjects and will be used for the analyses of efficacy endpoints on the face.

### 7.3.2 Per Protocol (PP) population

The PP population is defined as any subjects in the ITT population who had compliance to the study treatment between 80% and 120% and assessments of the primary endpoint at Baseline and Week 24, without any major deviations that could have a significant effect on the efficacy of the study treatment (e.g. errors in treatment assignment, use of prohibited medications). The PP population will be used for a sensitivity analysis of the primary endpoint.

### 7.3.3 Safety (SAF) Population

The SAF population is defined as comprising the ITT population subjects who applied/took the study drug at least once and will be used for all safety analyses.

GALDERMA R&D RD.06.SPR.204245 V00 18AUG2021 Page 72 of 104

# 7.4 Statistical Analysis

The main objective of this study is to evaluate acne-induced hyperpigmentation during the treatment of acne vulgaris subjects treated with trifarotene 50  $\mu$ g/g cream versus vehicle over 24 weeks.

## 7.4.1 General Methods

All data collected will be summarized by descriptive statistics and frequency tables as appropriate.

# 7.4.2 Demographics and Subject Disposition

Subject demographics and Baseline characteristics will be summarized with descriptive statistics and frequency tables as appropriate. Subject disposition will be summarized with the number of subjects in each population, the number and percentage of subjects who complete the study, along with the number and percentage of subjects who do not complete the study for each discontinuation reason as specified on the eCRFs.

# 7.4.3 Efficacy Analysis

[figure not shown]
The hypothesis test for the primary efficacy endpoint will be evaluated on the ITT population at the significance level  $\alpha = 0.05$ .

# 7.4.3.1 Primary Efficacy Endpoint

Absolute change from Baseline in PIH Overall Disease Severity scores of the face will be
analyzed at Week 24 using an ANCOVA with treatment, analysis center and Baseline score
as fixed effects; the p-values for the treatment comparison, estimates of the treatment
difference and the 95% confidence interval of the difference will be generated from the
ANCOVA model.

